10.3.3 Vital Signs

Vital sign data plots will be produced to graphically display data summaries. Each vital sign that is presented will include the time windows “Baseline”, “Day 1”, “Day 2-7 Combined”, and “Day 8-10 Combined.”

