10.3 Follow-up Procedures

10.3.1 Day 16 Post Randomization (± 4 days)

1. Every effort should be made to obtain safety labs Day 16 (± 4 days) after the first dose to include ALT, AST, alkaline phosphatase, total and direct bilirubin, and WBC with differential. A separate study sample is not required if these labs are obtained at Day 16 (± 4 days) after the first dose per standard of care.
2. Perform physical examination including weight, HEENT, heart, lungs, abdomen, skin, and extremities.
3. Perform vital signs (blood pressure, heart rate, respiratory rate, and temperature).
4. Document standard-of-care safety labs as described in Section 10.4.1.
5. Document microbiology assessments as described in Section 10.4.2.
6. Document radiological imaging as described in Section 10.4.3.
7. Document non-pharmacologic treatments as described in Section 10.4.3.
8. Review and record any AEs and SAEs as described in Section 12.1. Every effort should be made to bring the subject back for follow up, but SAEs must be collected via phone/other media if the subject is unable or unwilling to return.
9. Perform clinical outcomes assessment.

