14.1.3 Safety Analysis

For the primary safety endpoints, the frequency and percentage of subjects with AEs and therapy not tolerated will be determined and 95% CIs calculated. Summaries will be calculated by treatment group for the overall safety population and stratified by age group.

Additional safety analyses include summaries of AEs, descriptive statistics of laboratory values, descriptive statistics of vital signs, and frequency distributions of abnormal physical examinations. Laboratory data, such as hematology and serum chemistry data, as well as safety data will be analyzed. Summary statistics for changes from baseline and shift tables will be presented. Continuous laboratory measurements will be described at each visit using descriptive statistics (mean, median, etc.); observed values and changes from baseline will be summarized. Laboratory tests reflective of liver toxicity (e.g., ALT, AST) will be further summarized in terms of the most extreme values and largest changes from baseline (in the appropriate direction) observed from start of study drug through the end of therapy. All analyses will include summaries for both treatment and active comparator.

Additional details of safety analyses will be included in the Statistical Analysis Plan (SAP).

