10.3 Additional Safety Analyses

Additional safety analyses include summaries of AEs, descriptive statistical summaries of abnormal laboratory values, frequency distributions and shift tables summarizing abnormal laboratory values, graphs of lab values and vital signs, and summaries of concomitant medications as well as prior medications. Pregnancy test results and non-pharmacological treatments will be listed but not summarized. These analyses will be presented in the safety population using intent-to-treat analysis. Summaries will be produced by treatment arm, drug route, and consolidated age groups (2 months - <6 years, 6 years – 17 years inclusive) with the exception of lab graphs and

shift tables. The lab graphs and shift tables will be summarized by treatment arm, with all age groups combined. Safety data will also be listed by treatment arm, age group, formulation (for solithromycin patients only), and subject, with relevant information such as values, normal ranges, and severity presented.

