14.4 Safety Data

Table 14.4.1	Proportion of Subjects Experiencing a Treatment Emergent Adverse Event or Discontinuing Study Drug Due to Related Adverse Event – By Treatment Arm and Age Group
Table 14.4.1.1	Proportion of Subjects Experiencing a Treatment Emergent Adverse Event or Discontinuing Study Drug Due to Related Adverse Event – By Treatment Arm, Age Group, and Formulation
Table 14.4.2	Overview of Adverse Events – By Treatment Arm, Consolidated Age Group, and Drug Route
Table 14.4.2.1	All Treatment Emergent Adverse Events by System Organ Class and Preferred Term – By Treatment Arm, Consolidated Age Group, and Drug Route
Table 14.4.2.1.1	Treatment Emergent Adverse Events by System Organ Class and Preferred Term, Excluding Infusion Site Adverse Events – By Treatment Arm, Consolidated Age Group, and Drug Route
Table 14.4.2.1.2	Treatment Emergent Infusion Site Adverse Events by System Organ Class and Preferred Term – By Treatment Arm, Consolidated Age Group, and Drug Route
Table 14.4.2.2	Overview of Serious Adverse Events – By Treatment Arm, Consolidated Age Group, and Drug Route
Table 14.4.2.3	Treatment Emergent Serious Adverse Events by System Organ Class and Preferred Term – By Treatment Arm, Consolidated Age Group, and Drug Route

Table 14.4.3	Shift from Baseline to Worst Post-Baseline Value: Hematology Tests – By Treatment Arm
Table 14.4.3.1	Abnormal Laboratory Results Summary: Hematology Tests – By Treatment Arm
Figure 14.4.3.2	Worst Post-Baseline vs Baseline Laboratory (Scaled by Normal Values): Hematology Tests – By Treatment Arm
Figure 14.4.3.3	Worst Post-Baseline vs Baseline Laboratory (Scaled by Normal Values): Hematology Tests – By Solithromycin Consolidated Age Group and Drug Formulation
Table 14.4.3.2	Shift from Baseline to Worst Post-Baseline Value: Chemistry Tests – By Treatment Arm
Table 14.4.3.2.1	Abnormal Laboratory Results Summary: Chemistry Tests – By Treatment Arm
Figure 14.4.3.2.2	Worst Post-Baseline vs Baseline Laboratory (Scaled by Normal Values): Chemistry Tests – By Treatment Arm
Figure 14.4.3.2.3	Worst Post-Baseline vs Baseline Laboratory (Scaled by Normal Values): Chemistry Tests – By Solithromycin Consolidated Age Group and Drug Formulation
Table 14.4.3.2.4	Summary of Liver Function Tests – By Treatment Arm
Table 14.4.3.2.5	Summary of Liver Function Tests – By Solithromycin Consolidated Age Group and Drug Route
Figure 14.4.4	Summary Plot of Vital Signs – By Treatment Arm

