16.2.9 Vital Signs

- Listing 16.2.9.1 Vital Signs

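### The SAP's vital-sign plots stop at Day 10, so the scheduled Day 16 readings and some comparator end-of-treatment readings enter no final summary, and the one planned figure is split by arm only, contrary to SAP 10.3

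*SAP*

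**What the plan says.** - **Windows.** SAP 10.3.3 plans plots of vital signs and fixes their time axis: "Each vital sign that is presented will include the time windows" Baseline, Day 1, Day 2-7 combined and Day 8-10 combined. Nothing later is named.
- **Outputs.** The SAP output list has one vital-sign figure, 14.4.4, "Summary Plot of Vital Signs – By Treatment Arm", and one listing, "Listing 16.2.9.1 Vital Signs". It has no vital-sign table.
- **Grouping in the SAP text.** SAP 10.3 counts "graphs of lab values and vital signs" among the additional safety analyses and then says: "Summaries will be produced by treatment arm, drug route, and consolidated age groups". The exception is narrow: "The lab graphs and shift tables will be summarized by treatment arm, with all age groups combined". Vital-sign graphs are not exempted.
- **Schedule.** Protocol Table 1, Protocol 10.3.1 and SAP Table 4 all place vital signs at the Day 16 (±4) visit and at the last day of treatment (+48 h).
- **Protocol analysis.** Protocol 14.1.3 lists "descriptive statistics of vital signs" among the safety analyses and leaves further detail to the SAP.

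**The concern.** Safety is the primary objective. The SAP carries adverse events (10.3.1) and liver-test extremes (10.3.2) through Day 16, yet vital signs from the same visit have no place in any final summary. The omission looks like an oversight.

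The late windows also treat the arms unequally. Solithromycin courses are short and fixed, while comparator courses run 5 to 10 days. Day 8-10 therefore holds different kinds of children by arm, and the readings that can fall off the end belong to the comparator arm.

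Heart rate is the vital sign with a documented drug signal: Protocol 5.2.2.2.2 reports an exposure-related rise in adults, peaking at 15 bpm after a supratherapeutic IV dose. Heart rate also varies strongly with age, as the protocol's tachycardia cut-offs of 100 to 160 bpm show. A plot of absolute values pooled from 2 months to 17 years, with no change from baseline, is a blunt way to look for such an effect. A programmer who follows the output list would also depart from the SAP's own text.

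**Working it through.** The plan states no figure for vital signs, so there is none to reproduce. The check has three parts.

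**1. Visit days against plot windows.** Day 1 is taken as the day of randomisation and first dose. Course lengths come from Protocol 7.3 and SAP 3.4.

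| Scheduled reading | Possible days | In a plot window? |
|---|---|---|
| Oral-start solithromycin: Day 5, +48 h | 5-7 | Yes, all in Day 2-7 |
| IV-start solithromycin: Day 7, +48 h | 7-9 | Yes, in Day 2-7 or Day 8-10 |
| Comparator, 5 to 8 days, +48 h | 5-10 | Yes |
| Comparator, 9 days, +48 h | 9-11 | Day 11 is not |
| Comparator, 10 days, +48 h | 10-12 | Days 11 and 12 are not |
| Day 16 visit, ±4 | 12-20 | None |

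The Day 16 visit overlaps the windows by zero days. Under this regimen, oral-start solithromycin children have no scheduled reading in Day 8-10.

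**2. SAP text against output list.** SAP 10.3 requires arm, drug route and consolidated age group, and exempts lab graphs and shift tables. Figure 14.4.4 gives arm only. The two cannot both be followed.

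**3. What pooling ages costs in precision (illustration).** The documents give no heart-rate SD, so these inputs are assumptions:
- Age-specific level: the tachycardia cut-offs in Protocol 10.9 serve as a proxy, namely 160, 140, 126.7 and 100 bpm for the four age groups. For 6 to <12 years, (4 × 140 + 2 × 100)/6 = 126.7.
- Equal shares of the four age groups.
- Within-age SD of 15 bpm (range 10-20).
- 75 versus 25 children: the 3:1 split of 100, which is the ceiling because SAP 2 reports fewer than a quarter of 400.

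The half-width is 1.96 × SD × √(1/75 + 1/25) = 1.96 × SD × 0.231.

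- *Pooled.* Between-age SD = 21.8. Total SD = √(15² + 21.8²) = 26.5. Half-width = **12.0 bpm** (10.9-13.4 over the SD range).
- *Two consolidated groups, combined.* Residual between-age SDs are 10 (from 160 and 140) and 13.3 (from 126.7 and 100). Mean residual variance = (100 + 177.8)/2 = 138.9. Total SD = √(225 + 138.9) = 19.1. Half-width = **8.6 bpm** (7.0-10.5).
- *Each consolidated group read alone* (37.5 versus 12.5 children; factor √(1/37.5 + 1/12.5) = 0.327). Under 6 years: 1.96 × 18.0 × 0.327 = 11.5 bpm. Ages 6-17: 1.96 × 20.1 × 0.327 = 12.8 bpm (unrounded inputs).

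A second set of assumptions uses 72 versus 24 children, within-age SD 12-20, three age mixes, and the age spread inside the 6 to <12 group retained. It gives 10.4-14.3 bpm pooled and 7.9-12.3 bpm consolidated, so pooling widens the interval by about 14-38%.

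**The case against.** The case for leaving the plan alone has several good parts.

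- **Confounding.** A reader might infer that age pooling hides or distorts a heart-rate shift. The documents do not support that. Randomisation is stratified by age (SAP 3.3) and the plots include Baseline, so pooling costs precision and does not bias the arm comparison. No interval or test on vital signs is planned, and the within-age SD is not in the documents.
- **Size of the gain.** Adjusting for all four age strata would bring the half-width to 1.96 × 15 × 0.231 = 6.8 bpm, but the consolidated grouping does not deliver that. Panels read one at a time (11.5 and 12.8 bpm) are no sharper than the pooled plot (12.0). Only combining them gains.
- **Day 16 and heart rate.** A reader might take Day 16 as the place to see the drug effect. With a half-life of about 7.5 h (Protocol 5.2.2.2.4), Day 7 to Day 12 is 120 h, or 16 half-lives. The adult peak came right after an 800 mg infusion. In Phase 3, tachycardia above 120 bpm with a rise of at least 15 bpm was slightly rarer than on moxifloxacin (1.3% versus 1.8%, Protocol 5.2.4.1). Day 16 matters for completeness and recovery.
- **Not reported.** The values are in Listing 16.2.9.1, and with fewer than 100 children a listing is readable. The DMC also receives aggregate vital-sign summaries (SAP 11), with unstated windows.
- **Day 8-10 holds only IV-start solithromycin children.** This cannot be said of the whole dataset. Amendment 2 records that 5 to 7 days was previously allowed for all formulations, and Protocol 7 still gives 5 to 7 days for oral dosing where 7.3 gives 5. Those passages need reconciling.
- **Curtailment.** SAP 2 cut analyses because of small age subgroups, and a plot of summaries does show descriptive statistics.

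All of this limits the consequence. It does not explain why a scheduled visit is dropped, why Day 11-12 readings have no window, or why the figure ignores the two consolidated groups that the SAP kept.

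**Conclusion.** The concern holds as a gap in reporting and an inconsistency inside the SAP. Three parts rest on the documents alone:

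- Scheduled Day 16 vital signs enter no final summary.
- Comparator readings on Day 11 or 12 fall outside every window.
- Figure 14.4.4 contradicts SAP 10.3.

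The protocol's descriptive statistics are also reduced to plots, with no change from baseline.

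The loss of precision is real in direction but illustrative in size: about 12 bpm pooled against about 8.6 bpm with the two consolidated groups combined. It rests on cut-offs used in place of mean heart rates, an assumed SD, equal age shares and 75 versus 25 children. How much change from baseline would add cannot be computed from the documents. No primary endpoint, sample-size figure or error rate is affected. The change is worth making because safety is the primary objective and the cost is very small.

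**What to change.** 1. In SAP 10.3.3, add a Day 16 (±4) window.
2. Add a last-day-of-treatment (+48 h) summary beside the day windows. It captures comparator readings on Days 11-12.
3. Plot and tabulate observed values and change from baseline (n, mean, SD, median, range) by arm within consolidated age group, and by drug route for solithromycin. This also meets Protocol 14.1.3.
4. Retitle Figure 14.4.4 to match the grouping in SAP 10.3, and add the table to the output list.

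The cost is SAP wording and a little programming; the data are already collected. There are two drawbacks to state in the report: cells will be small after early termination, and the end-of-treatment summary falls on different days in the two arms, so it should be read alongside the day-based windows.

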10.3.4 Prior and Concomitant Medications

Prior and concomitant medication use will be tabulated by generic drug name. Prior medications and concomitant medications generic name and anatomic therapeutic chemical classification (ATC) level will be coded using the September 2015 version of the World Health Organization Drug Dictionary (WHODD) Enhanced.

10.3.5 Pregnancy Tests

Pregnancy test results at baseline and any other reported will be listed for female participants of child-bearing potential.

10.4 Secondary Efficacy/Clinical Outcomes

Evaluation of clinical signs and symptoms of CABP, requirement for additional or alternative antimicrobial therapy, and efficacy will be performed by a blinded investigator or designee at the site. Outcomes will be assessed at the following time points:

- Baseline clinical signs and symptoms assessment
- Clinical improvement on Day 3 - 4. If the subject is discharged from the hospital prior to Day 3, assessment may be recorded on Day 2.
- Clinical improvement on the last day of treatment (+48 hours)
- Clinical cure during short-term follow up at 16 days (\pm 4 days) after randomization (secondary efficacy endpoint). This assessment will be conducted if information is available per standard of care and may be recorded from the medical record via phone or other media.

Efficacy will be quantified as a binary variable at each timepoint listed above using the algorithm specified in Appendix 2. Clinical improvement is defined as improvement (compared to baseline) of at least 1 of the presenting signs and symptoms of CABP with no deterioration in any presenting sign or symptom of CABP (compared to baseline), no development of new sign or symptom of CABP, and no requirement for additional or alternative antimicrobial therapy. Clinical cure is defined as resolution of all presenting signs and symptoms of CABP (excluding cough), no development of new sign or symptoms of CABP, and no requirement for additional antimicrobial therapy. Clinical improvement and cure will be determined using the specific signs and symptoms data recorded on the eCRF, as well as a separate question on the eCRF concerning additional antimicrobial therapy. These questions will be completed by the blinded investigator (or potentially unblinded investigator in the case of screening evaluation), who will be supplied with information according to the blinded investigator plan.

Efficacy will be evaluated in the randomized population, and subjects will be evaluated in the treatment group to which they were randomized regardless of actual treatment received (Intention-To-Treat analysis). The main analysis of efficacy at each time point will include subjects with efficacy evaluated at that time point (complete case analysis). The frequency and percentage of subjects achieving each efficacy end point will be determined, and a 95% Clopper-Pearson (exact) confidence interval calculated. Summaries will be calculated by treatment arm for the overall randomized population and by treatment arm stratified within consolidated age group. This study is not powered for comparison of efficacy end points between treatment groups.

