10.7 Clinical Improvement Definition (Early Clinical Response and End-of-Treatment Response)

Clinical improvement is defined as improvement of at least 1 of the presenting signs and symptoms of CABP with no deterioration in any presenting sign or symptom of CABP, no development of new sign or symptom of CABP, and no requirement for additional or alternative antimicrobial therapy.

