10.8 Clinical Cure Definition (Day 16 Post Randomization [±4 Days])

Clinical cure is defined as resolution of all presenting signs and symptoms of CABP (excluding cough), no development of new sign or symptoms of CABP, and no requirement for alternative antimicrobial therapy.

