The minimum weight requirement of 60 kg for solithromycin capsule dosing in the 12 to 17 year old age group has been removed. This is supported by PK modeling efforts from Phase 1 studies as well as by safety data from more than 100 adult patients <60 kg who received solithromycin in completed pneumonia studies (Cempra Phase 3 studies and Toyama Phase 2 study).

“Clinical failure or lack of efficacy” has been added as a reason for discontinuation from study drug, and “withdrawal of consent due to an adverse experience” has been added as a reason for discontinuation from study. These additional reasons will better categorize patient disposition.

Language has been modified in some sections to improve the clarity of the protocol requirements and procedures, and to correct minor typographical errors. Typographic corrections, including grammatical and punctuation errors, are not shown.

New/revised text is in ***bolded italics***. Deletions are identified by ~~strikethrough~~.

SIGNATURE PAGE

~~[name]~~ **[name]**, MD
Sr. Director, Pediatric Clinical Research

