10.8 Clinical Cure Definition (Day 16 Post Randomization [\pm 4 Days])

Clinical cure is defined as resolution of all presenting signs and symptoms of CABP (excluding cough), no development of new sign or symptoms of CABP, and no requirement for ~~additional~~ *alternative* antimicrobial therapy.

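### The Day 16 cure sentence in SAP 10.4 excludes *additional* antimicrobial therapy and protocol 10.8 excludes *alternative* therapy, so a resolved child could be scored differently; the SAP declares no departure

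*SAP*

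**What the plan says.** **Cure, protocol 10.8 (current text).** All presenting signs and symptoms except cough have resolved, with "no development of new sign or symptoms of CABP, and no requirement for alternative antimicrobial therapy".

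**Cure, SAP 10.4.** The same definition, ending "no development of new sign or symptoms of CABP, and no requirement for additional antimicrobial therapy".

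**Improvement, both documents.** Protocol 10.7 requires "no requirement for additional or alternative antimicrobial therapy", and SAP 10.4 uses the same pair of words for improvement.

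**How SAP 10.4 obtains the item.**
- Its opening sentence has the evaluation of "requirement for additional or alternative antimicrobial therapy, and efficacy will be performed by a blinded investigator or designee at the site".
- Improvement and cure are then derived from the recorded signs and symptoms plus "a separate question on the eCRF concerning additional antimicrobial therapy".
- Each time point becomes a binary variable "using the algorithm specified in Appendix 2".

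**History.** The Amendment 2 log in protocol Appendix A shows the edit to 10.8 as "no requirement for ~~additional~~ *alternative* antimicrobial therapy". It is used here only to date the change. The Amendment 2 rationale does not mention this edit; the nearest statement is general: "Language has been modified in some sections to improve the clarity of the protocol requirements and procedures".

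**Related rules.** Protocol 8.3.1 lets either arm add expanded gram-positive coverage when empiric MRSA treatment is wanted. SAP 3.4 counts certain comparator drug changes as efficacy failure.

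**The concern.** Cure at Day 16 is a named secondary efficacy endpoint, reported in Table 14.5.1. The SAP says in section 2 that it rests on the protocol in force when it was finalized. Its cure sentence nevertheless carries the word that Amendment 2 had replaced a little over six months before SAP 1.0, and SAP 1.1 (14 May 2018) still has it. Other Amendment 2 changes did reach the SAP, including the Day 28 follow-up and the fixed 5-day and 7-day solithromycin courses. From the text alone one cannot tell whether the cure wording is a carry-over, a loose label or a choice.

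Adding an antibiotic and replacing one are different events, and the plan expects the first to occur in both arms. If the two cure sentences are applied as written, they disagree on some children. A reader of the cure rate would then not know which definition produced it.

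**Working it through.** The plan gives no figure for this point, so the check is a side-by-side reading followed by a bound on size.

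**1. Literal comparison.** Take a child with all presenting signs resolved (cough aside) and no new sign. Cure then depends only on the antimicrobial condition.

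| Therapy required | Protocol 10.8 | SAP 10.4 cure sentence, literal |
|---|---|---|
| Neither | Cured | Cured |
| Add-on only | Cured | Not cured |
| Replacement only | Not cured | Cured (see step 2) |
| Both | Not cured | Not cured |

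The sentences disagree in two of four cells, in opposite directions.

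**2. What narrows the replacement cell.** In the comparator arm, SAP 3.4 already counts as efficacy failure a change from oral to IV, or a change of drug by the same route within the first 5 days. A switch from IV to a different oral comparator is not a failure unless the site records premature discontinuation. The rule does not cover solithromycin, later same-route changes, or add-on therapy in either arm. The opening of SAP 10.4 also names both kinds of therapy. This cell is therefore less certain than the add-on cell.

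**3. What narrows both cells: timing.** The cure window is 16 ± 4, that is Day 12 to Day 20. The last planned dosing day is Day 7 at most for solithromycin and Day 10 at most for comparator (SAP 3.1). An antibiotic first needed inside the window has no study drug to be added to or to replace, so the two words largely converge. The disagreement concerns mainly therapy started during dosing.

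**4. Size.**
- SAP section 2 puts enrolment below one quarter of 400: 400/4 = 100, so at most 99.
- Assuming the 3:1 allocation held: 99/4 = 24.75, about 25 comparator; 99 × 0.75 = 74.25, about 74 solithromycin.
- One reclassified child: 1/25 = 4.0 points; 1/74 = 1.35, about 1.4 points.
- Efficacy is analysed on complete cases. If only 15 to 20 comparator children were evaluated (assumed range): 1/15 = 6.7 points to 1/20 = 5.0 points.

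**5. Scale against the planned interval.** The 95% Clopper-Pearson limits for illustrative counts are 21/25 = 84.0% (63.9 to 95.5) and 20/25 = 80.0% (59.3 to 93.2). The first interval is 95.5 − 63.9 = 31.6 points wide, so a 4-point shift is small beside it.

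**The case against.** The strongest reply is that the prose sentence does not score anyone. Appendix 2 does, and its absence from the supplied text is not a gap in the plan. It may apply *additional or alternative* throughout. This stands, and it limits the claim to what could happen under a literal reading. A reader might infer that children were in fact misclassified; the documents do not show that.

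A second reply is that the SAP uses *additional* loosely. One eCRF question, labelled with that word alone, serves improvement as well as cure, and improvement is defined with both words. This also stands. A reader might infer from the improvement definitions that the two words always mark distinct conditions, or that the SAP deliberately restored the older endpoint. The shared eCRF label undercuts the first inference, and nothing in the SAP supports the second. Loose wording is an explanation, though, and it does not make the two cure sentences agree.

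A third reply is that SAP 3.4 already handles switched children. It does so for some comparator changes only, and it says nothing about add-on therapy.

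A fourth is that a single statistical group runs every analysis and checks outputs against the SAP, so no second analyst will score from protocol 10.8. That is fair. What remains is that a reader comparing the report with the protocol cannot tell which definition was applied.

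**Conclusion.** The point holds as a minor inconsistency in current text. Protocol 10.8 and the SAP 10.4 cure sentence state different antimicrobial conditions for the same secondary endpoint, and no departure is declared. The clearest case is a resolved child who required only add-on therapy. Even there, the documents do not say whether permitted empiric gram-positive coverage counts as a requirement for additional therapy.

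The number of children affected is unknown and may be zero. The per-child shifts rest on an enrolment of 99 (the maximum) and a 3:1 split that the documents do not confirm for the final sample. A reader might infer that the efficacy conclusions are at risk. They are not: the endpoint is descriptive, the study is not powered to compare efficacy, the exact intervals are wide, and the primary safety endpoints do not use this definition. One child could change the reported rate but not what can be concluded from it.

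**What to change.** 1. Put the protocol 10.8 wording into the SAP 10.4 cure sentence. Alternatively, keep the SAP wording and declare and justify the departure in the SAP and the clinical study report. SAP section 2 already commits the report to describing deviations.
2. Check that Appendix 2, the use of the eCRF antimicrobial question and the SAP 3.4 rule on comparator changes all follow the chosen definition, with the blinded investigator's assessment kept as the source.
3. State in a footnote to Table 14.5.1 which definition produced the cure rate. A sensitivity row under the other reading is optional, and possible only where the data separate add-on from replacement therapy.

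The cost is one word or one declared departure, a consistency check with perhaps a small derivation change, and a footnote. No new data are needed. The downside is that the reported rate may shift slightly in either direction. If the eCRF question cannot separate the two cases, the ambiguity can be disclosed but not resolved.
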